2.3 Diagnosis of BV

The complex etiology of BV can contribute to an inaccurate diagnosis, especially in asymptomatic individuals in late pregnancy.(20) Microscopy of vaginal fluid has been a mainstay of office-based testing for vaginitis. A clinical diagnosis using Amsel criteria allows for a diagnosis at the bedside with prompt treatment. In addition, microscopic testing with Gram stain using Nugent score is considered the gold standard.(21) However, both methods require skilled staff and time and suffer from reduced sensitivity and specificity. Inaccurate BV results may lead to misdiagnosis and delays in treatment. NAATs can identify and differentiate between organisms associated with vaginitis and be a convenient point of care test, but remains to be validated in pregnancy.

Nucleic acid amplification tests (NAATs) to diagnose BV have been developed and its performance in comparison to gram stain and microscopy has been assessed outside of pregnancy among symptomatic and asymptomatic women. The Labcorp NAATs test includes Atrobium vaginae, BVAV-2, and Megasphaera-1, and in recent study of 100 non-pregnant individuals with and without vulvovaginal symptoms in gynecologic care, this test had a lower sensitivity but similar specificity (80 and 98%) compared to Amsel (99 and 99%) and gram stain (83 and 96%).(22) These studies have generally been conducted among samples of women seeking gynecologic care, family planning services, or testing for sexually transmitted diseases.

Because the performance of a diagnostic test varies according to the characteristics of the study population, studying the performance of a NAAT test in pregnancy is warranted. The prevalence of BV is known to decrease in late pregnancy in the setting of a changing hormonal milieu. The ideal test for women presenting with symptoms of vaginitis would have high sensitivity and specificity and would be available at the point of care.

2.4 Treatment of BV and obstetrical and surgical outcomes. The benefits of treating BV in pregnancy have been evaluated, but have been done in the setting of preterm birth prevention, and not to prevent peripartum infection. Hauth et al reported 18% decrease in the rate of preterm labor following treatment of BV in the 2nd and early 3rd trimesters in women with previous

history of preterm labor (14). However, another randomized controlled trial failed to demonstrate benefit in low-risk women.(19) In the setting of scheduled hysterectomy for benign indications, pre-procedure treatment of BV been associated with 3-fold decrease in the incidence of post-hysterectomy cuff cellulitis (11% vs 34%). Persson et al. noted a decrease in wound infections in patients with BV from 8% to 25% (18).

2.5 Current standard of care for BV management in pregnancy. Current standard of care does not involve screening for or treating BV without symptoms of vaginitis in pregnancy. Similarly, the standard of care at OSUWMC does not involve screening for or treating BV in pregnancy. The current practice at our center is to screen for BV in women presenting with preterm contractions as part of a preterm labor evaluation or for those women presenting with symptoms consistent with vaginitis. We use the Amsel criteria to screen for BV in this population and if they test positive, and the decision is made to discharge the patient, a 7-day course of metronidazole is prescribed, 500 mg twice daily. Stated otherwise, we do not routinely screen for or treat BV in late 3rd trimester as a prophylaxis prior to induction or spontaneous labor, unless the patient reports vaginal discharge or other symptoms suggestive of BV.

2.6 Treatment regimens for BV in pregnancy. Multiple regimens have been suggested for treatment of BV in pregnancy including:

- 1) metronidazole 500 mg twice daily for 7 days,
- 2) metronidazole 2 g once, and
- 3) clindamycin 300 twice daily for 7 days.

Metronidazole is classified as FDA category B, and current data does not suggest an increased risk of congenital anomalies with metronidazole use in pregnancy (1). Pharmacokinetics of metronidazole are not affected by pregnancy (13). Koss et al did not find any association between metronidazole use and preterm birth, low birth weight or congenital anomalies (2). Given the high prevalence of BV in our population and the potential of BV treatment to decrease the incidence of peripartum infection as well as other maternal and neonatal complications, there is public health benefit in proceeding with investigating the effects of treatment of BV in early labor. While prior studies have focused on screening and treating BV in pregnancy to prevent preterm birth, no studies have been performed to evaluate the benefits of treating BV in the late 3rd trimester prior to delivery to prevent peripartum infection.

3. CONCISE SUMMARY OF PROJECT

3.1 Primary Research Question:

Does treatment of BV with 7-day course of metronidazole >34 weeks decrease the incidence of peripartum infection?

Hypothesis: Treatment of BV will reduce the incidence of peripartum infection, namely chorioamnionitis, endometritis, and SSI.

3.2 Secondary Research Questions

3.2.1: Does treatment of BV with 7-day course of metronidazole >34 weeks decrease the incidence of Gram stain +ve for BV at time of admission for labor?

[figure not shown]
Hypothesis : Treatment of BV will reduce the incidence of +ve Gram stain for BV at time of admission for labor.

3.2.2: Does treatment of BV with 7-day course of metronidazole >34 weeks decrease the incidence of neonatal complications including neonatal sepsis and NICU admission?

Hypothesis : Treatment of BV will reduce the incidence of neonatal complications.

3.2.3: Hypothesis : Does treatment of BV decrease utilization of health care services including maternal ER visits, postpartum clinic visits, OB triage visits, and postpartum hospital readmissions?

Hypothesis: Treatment of BV will reduce health care services utilization

4. STUDY DESIGN:

4.1 Study enrollment: We propose a double-blinded, placebo controlled, multi-center randomized trial of 482 pregnant women who are diagnosed with BV in late 3rd trimester (>34 weeks). During routine clinic visit after 34 weeks, prospective patients will be counseled about the study. Patients who agree to be enrolled, will sign informed consent.

Following enrollment, patients will be screened for BV. Those patients who are BV positive, will be randomized to receive either metronidazole 500 mg BID orally for 7 days or identically appearing placebo. The PI, Co-Investigators or study coordinators will be responsible for the informed consent.

1500 participants will be enrolled for screening to randomize 482 participants.

4.2 Study sites: This will be a multi-center, double-blinded randomized clinical trial. The primary site will be OSUWMC. The secondary center will be University of Texas Medical Branch, Galveston, Texas, and may include additional medical centers over time. The study period will be between November 2020 to September 2022. The number of subjects studied will be 482 patients. If a patient wishes to withdraw from study after randomization and receipt of study medications, no additional interventions will be performed, but we will collect study outcomes with patient consent as this is intent to treat study and patients' outcomes will be analyzed in the group they were assigned to.

Neither the patient nor provider will be aware of treatment assignment. No significant adverse effects are expected with the use of antibiotics in the study population. As with any other instance in which antibiotics are administered, there is a chance of an allergic or other adverse reaction. The patient will receive standard inpatient monitoring during the labor course and in the postpartum period, and so any immediate adverse reaction can be promptly detected. The study period will be November 2020 to September 2022. The number of subjects studied will be 482 patients. If a patient wishes to withdraw from study after randomization and receipt of study medications, no additional interventions will be performed, but we will collect study outcomes as this is intent to treat study and patients' outcomes will be analyzed in the group they were assigned to.

5. INCLUSION CRITERIA:

- Pregnant women 18 to ≤50 years with the ability to give informed consent.
- Patients expected to have a vaginal delivery with no obstetric contraindication for vaginal delivery at time of screening.
- Gestational age ≥ 34 weeks

6. EXCLUSION CRITERIA:

- Plan for elective cesarean delivery
- Allergy or contraindications to metronidazole
- Receipt of metronidazole or clindamycin on admission for delivery for other indications.
- Hemodialysis
- Severe liver dysfunction
- Patient reports BV to nurse or clinician provider at current clinic visit or has been treated for BV within the past 3 months.

7. STUDY PROCEDURES:

7.1 Randomization and enrollment in clinic at or after 34 weeks: After obtaining informed consent, patients with a plan for vaginal delivery will be screened for BV by self-collecting 2 vaginal swabs for Gram stain, and Amsel criteria. A 3rd swab will be collected and stored at -80C for future microbiome analysis at the end of the study. The 3rd swab for future microbiome analysis is associated only with this study. When all study is complete, we will run the analysis to see if there is an association between microbiome and peripartum infections. The reason for storing the specimens and running them at the end is to decrease the cost. Patients with positive Amsel criteria will be eligible for randomization. Randomization and providing the patient with medications will be done at the same visit.

7.2 Clinical diagnosis of BV:

Amsel criteria are:

- Homogenous thin grayish-whitish discharge that coats vaginal mucosa
- Vaginal PH >4.5
- Positive whiff-amine test, presence of fishy odor on adding a drop of 10% KOH
- Clue cells on wet mount

Patients who have at least 3 out of 4 of Amsel criteria will be considered positive for BV and will be randomized into either a control group or study group. Patient will be asked to characterize their vaginal discharge. Nitrazine paper will be used to assess PH. Saline will be added and light microscopy will be used to assess for clue cells and 10 % KOH will be added for whiff test.

Gram stain for BV: A gram stain will be collected from participants in clinic at time of screening and will be sent to the lab.

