7.3 Confirmation of therapy success

Following completion of therapy, patients admitted to labor and delivery will have 1 additional swab. The swabs can be collected by the provider during performing normal labor exam or it can be self-collected by the patient. This swab will be sent to the lab for another gram stain. However, results will not be used for clinical decision guidance. It will be used for analysis later.

7.4 Clinical care: The care of patients in the remaining antepartum period, intrapartum period, including the method of induction or augmentation of labor will be according to standard of care at the participating site, and per the managing clinical team. After a subject who meets inclusion criteria agrees to participation in our study, the obstetric team will contact one of the investigators. Signed informed consent will be obtained by the PI, Co-Investigators or study coordinators. The total participation time in the study will be considered terminated at 6 weeks postpartum. No additional antepartum or postpartum will be required for the study, only routine visits will be recommended.

7.5 Data collection: The data collected will be kept on a password-secured Ohio State Wexner Medical Center (OSUWMC) computer. An encrypted USB flash drive will be used to transfer data. The data will be linked to the patient by patient's MRN number. This identifier is needed to access and analyze demographic data. During analysis of the data, all identifiers will be deleted.

7.6 Informed consent. Under the direction of the PI, trained research staff will be available 24/7 to screen and consent patients according to study protocol. Patients will be enrolled in clinic at or after 34 weeks gestation.

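### The labor Gram-stain comparison does not use the screening Gram stain, so it cannot give a clearance rate and may lose some contrast and precision

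*Combined protocol and SAP*

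**What the plan says.** All references are to the combined protocol and SAP.

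- **Entry test.** Section 7.1: "Patients with positive Amsel criteria will be eligible for randomization". Section 7.2 sets the threshold: "Patients who have at least 3 out of 4 of Amsel criteria will be considered positive for BV and will be randomized".
- **Screening stain.** Section 7.2: "A gram stain will be collected from participants in clinic at time of screening and will be sent to the lab".
- **Labor stain.** Under the heading "7.3 Confirmation of therapy success", one swab is taken at labor admission: "This swab will be sent to the lab for another gram stain". The text then says only that it will be analyzed later and will not guide care.
- **Question and hypothesis.** Section 3.2.1 asks whether treatment will "decrease the incidence of Gram stain +ve for BV at time of admission for labor", and its hypothesis is "Treatment of BV will reduce the incidence of +ve Gram stain for BV at time of admission for labor". Neither mentions the screening result.
- **Other use of the screening stain.** Secondary aim 1 (section 1.2) looks at peripartum infection by Gram-stain result at randomization and at labor. The outcome there is infection, not clearance.
- **Analysis.** Section 13 has no analysis specific to the Gram-stain outcome. It allows regression adjustment only where baseline variables turn out unbalanced. Section 7.14 does not list the outcome, and no section says which stain result counts as positive.

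**The concern.** Women are selected with one test and their response is read with another. Some Amsel-positive women may be Gram-negative at randomization. A negative labor stain in such a woman shows no change, so labor positivity alone cannot say how often a positive stain became negative.

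This matters mainly for interpreting the primary result. If infection rates do not differ, the investigators will want to separate a drug that did not clear BV from clearance that did not prevent infection. That calls for a clearance rate, which needs both stains. Both are collected, but the plan joins them only for the infection outcome.

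There is also a cost in efficiency. The screening stain is likely to predict the labor stain strongly. Randomization will usually balance it, so under section 13 it would usually be left out of the model.

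**Working it through.** **The plan's own figure.** The only sample size concerns the primary composite: 17% against 8.5%, two-sided alpha 0.05 (sidedness is not stated), 80% power.

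n = [1.960·√(2·0.1275·0.8725) + 0.842·√(0.17·0.83 + 0.085·0.915)]² / 0.085² = 240.5, so 241 per group and 482 in total, as stated. The plan gives no rate, effect or power for the Gram stain, so nothing below alters 482.

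**Inputs for the discordant share**
- Sensitivity and specificity from section 2.3, in non-pregnant women: the NAAT is "compared to Amsel (99 and 99%) and gram stain (83 and 96" percent).
- Prevalence of at least 30% (section 14). Section 2.3 says prevalence falls in late pregnancy, so 10% is added as an assumed low value.

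**Reading A: each pair is the test's own accuracy, with errors independent given true BV status**
- At 30%: P(Gram+ | Amsel+) = (0.30·0.99·0.83 + 0.70·0.01·0.04) / (0.30·0.99 + 0.70·0.01) = 0.24679/0.304 = 0.812. Gram-negative at screening: 18.8%, or 91 of 482.
- At 10%: 0.08253/0.108 = 0.764. Gram-negative: 23.6%, or 114 of 482.
- Correlated errors would lower these shares.

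**Reading B: Amsel's 99/99% was measured against Gram stain**
- At 30%: 0.70·0.01/0.304 = 2.3%, or 11 of 482.
- At 10%: 0.90·0.01/0.108 = 8.3%, or 40 of 482.
- Section 2.3 names no reference standard. Reading B needs Amsel to have been scored separately from the Gram-stain row, because a test scored against itself would show 100%. It is the low end of the range.

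**Effect on the contrast at the 19% share.** Labor positivity rates are not in the documents. Assume 70% on placebo and 30% on drug where the stain can detect BV, a 40-point difference, and 10% in both arms otherwise.
- *Screening-negative women stay largely negative:* placebo 0.81·0.70 + 0.19·0.10 = 0.586; drug 0.81·0.30 + 0.19·0.10 = 0.262. Difference 32.4 points, a loss of about 8.
- *Stain misses are independent between occasions:* under reading A, most discordant women truly have BV: 0.30·0.99·0.17 / (0.30·0.99·0.17 + 0.70·0.01·0.96) = 0.05049/0.05721 = 88%, about 80 of 91. They can test positive at labor like any other infected woman. Only the 2.3% without BV dilute: 0.977·40 = 39.1 points, a loss of about 1.

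**Effect on power.** This takes the unfavorable case: a share of 18.8%, screening-negative women all remaining negative, and a labor stain from every woman.

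| Labor positivity if positive at screening (placebo / drug) | Difference, all randomized | Power, 241 per arm | Power, 196 screening-positive per arm |
|---|---|---|---|
| 70% / 30% | 32.5 points | about 100% | about 100% |
| 70% / 50% | 16.2 points | 94.8% | 98.3% |
| 60% / 50% | 8.1 points | 43.3% | 51.2% |

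The risk ratio is unchanged in each row (0.43, 0.71, 0.83), because screening-negative women add no positives to either arm. If labor negativity were read as clearance in the 70%/50% row, it would be 43.2% and 59.4% where true clearance is 30% and 50%.

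**The case against.** The comparison in 3.2.1 is a proper intention-to-treat question. It covers all randomized women, the same Amsel-positive population as the primary outcome, and any discordance falls on both arms alike. The test is unbiased and type I error is not inflated. Dilution exists only relative to another estimand, clearance among screening-positive women. Secondary aim 1 already brings in the randomization stain, and both stains are collected, so nothing is irretrievably lost. All of this stands.

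Two stronger readings are tempting, and the documents support neither.

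- A reader might infer that women already Gram-negative at screening are counted as therapy successes in both arms. No such rule is written. The success wording occurs only in the 7.3 heading, and the text beneath leaves the analysis open. What can be said is that success is undefined.
- A reader might infer that section 2.3 establishes that a fifth of women are discordant and that the treatment difference shrinks in proportion. The share depends on an unstated reference standard and on prevalence. The full shrinkage also requires that the stain misses the same women on both occasions. Under the model that yields 19%, most discordant women do have BV, and with independent misses the loss is about 1 point.

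The objection does not remove two gaps. Aim 1 addresses infection, so no planned analysis gives clearance. And the section 13 rule leaves out a predictive baseline measurement unless it happens to be imbalanced.

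**Conclusion.** The point holds as a gap in one secondary analysis. The planned comparison is valid, but it cannot yield a clearance rate, and it gives up some absolute contrast and precision to the extent that women are Gram-negative at screening and remain so.

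The size is uncertain. The discordant share runs from about 2% to 24%, depending on how section 2.3 is read and on prevalence. At 19%, the loss is about 1 to 8 points of an assumed 40. In the unfavorable case, power is unaffected for a large effect and about 8 percentage points lower than in the screening-positive subset for 60% against 50%. These figures rest on non-pregnant accuracy data, on independent errors between Amsel and Gram stain, and on labor positivity rates that I assumed. The primary composite and the sample size of 482 are untouched.

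**What to change.** - **Section 3.2.1:** keep labor Gram-stain positivity in all randomized women as the main comparison, and adjust it for the screening Gram-stain result whether or not the arms are imbalanced. A risk difference stratified by the screening stain would keep the absolute scale. Exempt this covariate from the imbalance condition in section 13.
- **Section 7.3:** add, as a supporting analysis, clearance by arm, defined as a negative labor stain among women Gram-positive at screening. Membership is fixed before treatment, so the randomized comparison is kept.
- State which Gram-stain result counts as positive, and report the number Gram-negative at screening by arm, so that the discordant share is observed rather than assumed.

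The cost is a few sentences and no new samples, and the text can be settled before unblinding. The small downside is that the clearance analysis uses only the screening-positive subset (about 81% of women under reading A at 30% prevalence). It may leave out some women with BV that the stain missed, which is why it should support the all-randomized comparison and not replace it.

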7.8 Randomization and Masking: After obtaining informed consent, women with BV will be randomized to either control or study group according to a randomization sequence that is computer generated and maintained by the investigational drug pharmacy. A study enrollment log with a study ID number, subject name and medical record number, will be used to track enrolled patients. The investigational pharmacy at OSUMC will be notified after randomization and study drugs or placebos will be sent as dictated by patient's randomization group.

7.9 Drug Administration and Dispensation. Once a subject is consented randomization will be performed by the OSUWMC's investigational drug pharmacy (IDS). The appropriate study drug according to the group assignment will then be dispensed by OSUWMC's investigational drug services (IDS) pharmacy as well. Patients will receive 7 days of metronidazole 500 BID oral or similarly appearing placebo. The 14 pills will be provided in a container. The IDS pharmacy will dispense the drugs, account for dispensing and stock number. Funding provided by the department will cover the cost of the medications, and the patient's insurance company will not be billed. Subjects will be instructed to bring the container to clinic next visit or on admission to labor and delivery to count remaining pills and assess adherence.

The subject will be included in the analysis by intent-to-treat.

7.10 Baseline Procedures. Routine Ante, intra- and postpartum care will be provided to patients according to the local standard of care. Patients' clinical providers who will be blinded to the study interventions. Trained and experienced research staff (also blinded to group assignment) will be responsible for screening patients in clinic for eligibility and for all research data abstraction. All data will be de-identified after collection and tracked only with a study ID number.

The PI and co-PI will review and validate the diagnosis for all patients identified to have the primary composite outcome, applying current CDC and other standard criteria. These reviews

will be conducted masked to treatment group. If there is uncertainty, a second investigator will review the chart, discuss with the PI as needed, and make a final determination regarding the outcome. Maternal and neonatal outcomes will be assessed in the hospital following delivery (on an ongoing basis until discharge) and at the routinely scheduled postpartum follow-up visits up to 6 weeks postpartum.

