
7.11. Study visits / Follow-up. Part of the standard of care, all postpartum patients are followed after delivery to assess any postpartum complications. Before the subject leaves the hospital, patients are usually given their follow up appointment. This will be documented in the datasheet, in order to ascertain follow up. Patients will be educated about the signs and symptoms of infection and other study outcomes and encouraged to call the study research team with any concerns. In addition, records of visits (to any hospital clinic or ER) prior to the routine postpartum visit will be obtained and reviewed to ascertain study outcomes (treating providers may also be called if clarifications are needed). Finally, if patient does not present to routine postpartum care, a research staff will call all patients at 6 weeks postpartum to inquire about occurrence of study outcomes. Newborn outcomes will be ascertained through initial discharge from hospital or up to 90 days or death, whichever occurs first. Readmissions and related diagnoses for infants will also be ascertained through medical records.

7.12. Withdrawals. Patients who withdraw from the study after randomization will be followed up to ascertain outcomes. Outcomes ascertained will be reported in intent to treat fashion.

7.13. Primary Outcome #1: Composite of chorioamnionitis, postpartum endometritis, SSI, wound infection, or other post Cesarean infections (occurring within 6 weeks after delivery) defined as follows. These outcomes will be defined and assessed by trained research staff and reviewed and validated by the investigators, all blinded to group assignment.

1) Chorioamnionitis: this will be diagnosed if patient develops: Fever (defined as either 2 readings of $\geq 38.0^{\circ}\text{C} / 100.4^{\circ}\text{F}$ 30 minutes apart or one reading $\geq 39.0^{\circ}\text{C} / 102.2^{\circ}\text{F}$) in the absence of any cause for fever PLUS one of the following: 1) fetal tachycardia (>160 for 30 minutes or longer), 2) Leukocytosis (> 15000 in absence of corticosteroids), 3) Purulent discharge from cervical os, 4) biochemical or microbiological changes of the amniotic fluid (positive gram stain, positive culture, low glucose, high WBC).(1)

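### The safety text relies on inpatient monitoring, but the drug is taken at home after a clinic visit and no symptom inquiry near dosing is described, so mild adverse events may be under-recorded in both arms

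*Combined protocol and SAP*

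**What the plan says.** The safety text in section 4.2 (Study sites) describes "standard inpatient monitoring during the labor course and in the postpartum period, and so any immediate adverse reaction can be promptly detected". Section 7.1 sets a different scene, a clinic visit at or after 34 weeks: "Randomization and providing the patient with medications will be done at the same visit". Section 7.9 specifies 14 pills over 7 days, and 7.3 describes the labor-admission swab as following completion of therapy.

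The contacts and sources from which an adverse event could be learned are these:

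- Section 7.4: "No additional antepartum or postpartum will be required for the study, only routine visits will be recommended".
- Section 7.9: women are told to "bring the container to clinic next visit or on admission to labor and delivery to count remaining pills and assess adherence".
- Section 7.10: "Maternal and neonatal outcomes will be assessed in the hospital following delivery (on an ongoing basis until discharge"), and at routine postpartum visits up to 6 weeks.
- Section 7.11: records of hospital, clinic and ER visits before the routine postpartum visit are reviewed, treating providers may be called, and women are invited to call the team. For a woman who misses postpartum care, "a research staff will call all patients at 6 weeks postpartum to inquire about occurrence of study outcomes"; the sentence can be read as covering non-attenders only or everyone.
- Section 8: the electronic chart is the one named source of research material.
- Section 10: adverse events are to be summarized and several data collection forms used. The forms are not shown.

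Section 7.14 lists allergic reactions (including rashes) and gastrointestinal symptoms as a maternal secondary outcome, with no time window and no method of asking. Section 9.3 gives expected rates on metronidazole: nausea 12%, diarrhea and abdominal pain 4%, hypersensitivity 5%, headache 18%.

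**The concern.** The safeguard named in 4.2 operates during labor and the postpartum stay. The exposure occurs at home, possibly weeks earlier. The two coincide only for women admitted within the 7 days.

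The rest of the plan does not clearly fill the gap. The one contact likely to fall close to dosing is described for adherence only, and the formal assessment of maternal outcomes begins after delivery. A woman who has two days of nausea or a faint rash and seeks no care may leave no trace in a chart, and what is not asked at the time cannot be recovered reliably later.

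At stake is the adverse-event outcome in 7.14. The trial tests treatment in a setting where, by section 2.5, asymptomatic women are currently not treated. Anyone weighing a change of practice needs absolute tolerability figures, and understated ones would make treatment look easier to take than it is.

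**Working it through.** **1. The plan's own figure.** With 17% versus 8.5%, two-sided alpha 0.05, 80% power and no continuity correction:

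n = [1.960·√(2·0.1275·0.8725) + 0.8416·√(0.17·0.83 + 0.085·0.915)]² / 0.085² = (0.9245 + 0.3937)² / 0.007225 = 240.5, so 241 per group and 482 in total.

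This matches section 13. Nothing below changes it; 241 serves only as the number treated.

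**2. Does the assurance fit the dosing?** Drug is supplied in clinic (7.1), the course lasts 7 days (7.9), and admission is described as following completion (7.3). For a woman on that path, inpatient monitoring covers none of the dosing days. For a woman admitted within 7 days of dispensing, it covers part of them. The documents do not give the share of women in each group.

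**3. How far from dosing are the scheduled inquiries?**

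- 6-week call: if the course starts no later than the day of delivery, the gap from the last scheduled dose is at least 42 − 7 = 35 days.
- Start at 34w0d, course complete at 35w0d, delivery assumed at 37, 39 or 41 weeks: the in-hospital assessment comes about 2, 4 or 6 weeks after the last dose, and the call about 8, 10 or 12 weeks after.

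These gaps apply to the 7.10 assessment and the 7.11 call only. The 7.9 contact may come sooner but has no stated symptom inquiry. The 7.11 record review has no stated earliest date, so as worded it can reach antepartum visits.

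**4. Expected events, if all 241 take the drug and the 9.3 rates apply.** Nausea 241 × 0.12 = 28.9; diarrhea and abdominal pain 241 × 0.04 = 9.6; hypersensitivity 241 × 0.05 = 12.1.

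**5. Effect of incomplete capture.** Let c be the fraction recorded, equal in both arms. Recorded rate = c·p; recorded risk difference = c·(p₁ − p₀); recorded risk ratio = c·p₁ / (c·p₀) = p₁/p₀, unchanged. The documents give neither c nor a placebo rate, so both are assumed; 4% is used for placebo nausea.

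| c | Recorded nausea, drug arm | Recorded rate | Risk difference (placebo 4%) | Risk ratio |
|---|---|---|---|---|
| 1.00 | 28.9 | 12% | 8.0 points | 3.0 |
| 0.75 | 21.7 | 9% | 6.0 points | 3.0 |
| 0.50 | 14.5 | 6% | 4.0 points | 3.0 |
| 0.25 | 7.2 | 3% | 2.0 points | 3.0 |

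With an assumed placebo rate of 3% the full-capture difference is 9.0 points, halving to 4.5 at c = 0.50; with 8% it is 4.0, halving to 2.0.

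**6. Against sampling error.** At 75% capture, 22 of 241 has a Wilson 95% interval of 6.1% to 13.4%, which still includes 12%. At 50%, 14 of 241 gives 3.5% to 9.5%, which does not. Mild loss would thus be hard to distinguish from chance, while heavy loss would not. This treats 12% as the true rate in this trial, although 9.3 offers it only as a general figure.

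**The case against.** The strongest reply is that the second half of the point argues from silence. Section 10 assigns responsibility for safety monitoring, requires an adverse-event summary and mentions several forms that the reader cannot see; they may already ask about symptoms. That stands, and it is why under-recording is put as a possibility.

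Nor are the existing routes negligible. The record review in 7.11 is open-ended at its start, providers can be called, and women may telephone the team. A reader might infer that reactions in general, including serious ones, would go undetected. The documents do not support that. Most of the allergic events named in 7.14 (anaphylaxis, angioedema, Stevens-Johnson) would lead to care and so to a record. The concern is confined to mild, self-limited gastrointestinal symptoms and mild rash.

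It can also be said that the trial calls itself pragmatic, adds no visits, uses a regimen the site already prescribes (2.5), and states no aim about tolerability, so light elicitation is a legitimate choice. That lowers the weight of the point but does not answer it: adverse events are a listed outcome, and 4.2 claims prompt detection.

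Two smaller matters should not be enlarged. Headache has the highest single percentage in 9.3 (18%) and is not named in 7.14, but 9.3 describes gastrointestinal effects as the most common, and the section 10 summary is not limited to the 7.14 list. Section 2.6 speaks of "proceeding with investigating the effects of treatment of BV in early labor", but its next sentence refers to late third-trimester treatment before delivery, so this is stray background wording.

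**Conclusion.** The point holds in two parts of different strength. The mismatch is textual and needs no assumption: the 4.2 statement does not hold for women who complete the course before admission, and it conflicts with 7.1, 7.3 and 7.9. Under-recording of mild events is an inference. It rests on the absence of any described symptom inquiry near dosing, and it would fall away if the unseen forms contain one.

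If it occurs, its size depends on a capture fraction that the documents do not give. Across assumed values of 75% to 25%, recorded nausea would be 9% to 3% against 12%, with the risk difference reduced in the same proportion. It would be wrong to conclude that the comparison between arms is biased on the ratio scale: outcome staff and providers are masked, and equal capture leaves the risk ratio roughly intact. It would equally be wrong to carry the point over to efficacy. The primary composite and the sample size of 482 are untouched. The change should be made because it is cheap and the lost information cannot be recovered afterwards.

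**What to change.** Reconcile the 4.2 sentence with clinic dispensing in 7.1 and 7.9, so that the text says how reactions during the outpatient course come to light. State in 7.10 or 7.14 when, how and by whom the listed adverse events are asked about.

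At the pill-count contact already planned in 7.9 (next clinic visit or labor admission), have blinded staff complete a short checklist of allergic and gastrointestinal symptoms covering the dosing week, identical in both arms. If the course is unfinished at that contact, complete the checklist at the next routine contact. Naming headache on it is optional, and the phrase in 2.6 can be tidied at the same time. If the existing forms already ask these questions, cite them and correct only the wording.

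The cost is one short form, a few minutes per participant and no new visit. Under 7.10, "Trained and experienced research staff (also blinded to group assignment) will be responsible for screening patients in clinic for eligibility", but the protocol does not say that they attend the pill-count contact, so some staff time may be needed. Where the contact falls at labor admission, recall will be weaker, by about 2 to 6 weeks in the 34w0d scenario above, so recording the date of inquiry would help interpretation.
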